4.4 Subject Withdrawal or Termination

In accordance with the Declaration of Helsinki and other applicable regulations, a subject has the right to withdraw from the study at any time, and for any reason, without prejudice to his or her future medical care.

Subjects may be discontinued or withdrawn from the study for a number of reasons, including but not limited to those listed below:

- AE(s) (SAE or non-serious)
- Death
- Lack of efficacy
- Lost to follow-up
- Non-compliance (with study drug or study procedures)
- Physician decision
- Pregnancy
- Protocol violation
- Study terminated by sponsor
- Subject withdrew consent
- Other, specify

Every effort should be made to complete the Week 10/ET visit should a subject discontinue prematurely from the study.

If a subject is lost to follow-up, every effort should be made to phone the subject approximately 30 days after last known contact with the subject in order to assess the subject's current status. All phone contact with the subject should be documented.

For subjects who continue to be followed for safety, SAEs should continue to be reported as described in [Section 7](#).

If a subject is discontinued from the study because of an AE, every reasonable attempt should be made to follow the subject until the AE resolves or until the Investigator deems the AE to be chronic or stable.

If a subject is discontinued from the study due to pregnancy, every reasonable attempt should be made to follow the subject through the first well-baby visit and to document that follow-up.

All SAEs will continue to be followed until such events have resolved or the Investigator deems them to be chronic or stable.

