6.2.8 Massachusetts General Hospital Sexual Functioning Index

Sexual functioning will be assessed using the MGH-SFI ([Labbate 2001](#)). This is a patient-facing questionnaire that quantifies sexual dysfunction into 5 functional domains ("interest in sex," "sexual arousal," "ability to achieve orgasm," "ability to maintain erection" [males only], and "sexual satisfaction"). Patients rate each item using a 6-point scale ranging from 1 (good function) to 6 (poor function). The time frame for this scale is the past month.

6.2.9 12-Item Short Form Health Survey

The SF-12v2 ([Ware et al., 1996](#)) is a patient-reported outcome measure that addresses the same 8 domains as identified in the SF-36v2. However, due to brevity of the assessment, the only 2 scores obtained from this assessment are composite scores representing physical

health and mental health composite summaries, PCS and MCS, respectively. The 8 domains that are measured include Physical functioning (PF), Role – physical (RP), Bodily pain (BP), General health perceptions (GH), Vitality (V), Social functioning (SF), Role – emotional (RE), and Mental health (MH). Composite scores are obtained for the PCS and MCS. An algorithm is used to generate the PCS and MCS for comparison to normative data. In normative data, the mean score is set to 50; thus, scores >50 indicate better physical or mental health than the mean and scores <50 indicate worse health. The time frame for this scale is the past 4 weeks.

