6.5.12 Week 10/Early Termination Visit

Subjects will have the following procedures completed:

- Physical examination
- Vital signs (sitting [at least 3 minutes] BP, pulse, respiratory rate, and temperature)
- Weight
- 12-lead ECG (single recording; before blood sampling or at least 30 minutes after blood sampling)
- Clinical laboratory tests
- Serum and urine pregnancy tests for all women of childbearing potential
- PK blood draw for pimavanserin, AC-279, and concomitant SSRI/SNRI levels
- Assessment of concomitant medications
- Assessment of AEs
- Scales listed in [Table 2](#) (HAMD-17, CGI-S and I, SF-12, SDS, DAI-10, MGH-SFI, KSS, BIS-11, SIS, C-SSRS, AIMS, BARS, and SAS)
 - The C-SSRS time frame is since last visit
- Study drug accountability

6.5.13 30 Day Follow-Up Visit

Subjects will have the following procedures completed approximately 30 days following Week 10/Early Termination:

- Assessment of concomitant medications
- Assessment of AEs

These assessments will be performed through a telephone contact with the subject, and should be completed for subjects that complete all study visits and those who discontinue prematurely from the study.

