9.4.3 Analysis of the Secondary Endpoints

Continuous secondary efficacy endpoints (CGI-S and I, SF-12, SDS, DAI-10, MGH-SFI, KSS, BIS-11, and SIS) will be analyzed using methods similar to those described above for the primary efficacy endpoint. For CGI-I, baseline CGI-S score will be used as the covariate in the MMRM model. For the SF-12, DAI-10, and MGH-SFI, which are assessed only at Baseline and at Week 5 of each stage, an analysis of covariance model with fixed effects for treatment group and baseline score will be used instead of the MMRM model.

For the binary secondary endpoints of treatment response and remission, inference will be based on a combined treatment effect, using data from both stages. Details will be provided in the SAP.

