5.3.1 Unscheduled Assessments

Both Scheduled and Unscheduled assessments, including the assessments at early termination visits, will be used for planned timepoint analyses. All assessments will be presented in data listings.

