12.3 Handling of Missing Data

The primary analyses of the primary and key secondary efficacy endpoints will be performed in 2 steps and the missing data issue is only involved in Step 1:

1. Data from Stages 1 and 2 will be analyzed separately assuming missing at random (MAR) using the stage-specific, direct likelihood-based MMRMs and scores that are missing, after any imputation of individual missing items as described in Sections 5.2.1 and 5.2.2, will not be imputed. The MMRM method is unbiased under the MAR assumption and can be thought of as aiming to estimate the treatment effect that would have been observed if all subjects had continued on treatment for the full study duration (EMA, 2009).
2. Weighted combination of statistics from the stage-specific MMRMs will be used to perform the hypothesis testing.

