13.3 Other Secondary Efficacy Analyses

ANCOVA analyses for the secondary efficacy endpoints in this section will be performed using (1) the observed values (i.e., missing data will not be imputed) and (2) the last observation carried forward (LOCF) method for missing data (Note: for subjects without post-Baseline values, the Baseline values will be carried forward).

Remission rate at the end of the two 5-week treatment periods

Remission is defined as a HAMD-17 total score less than or equal to 7. Missing HAMD-17 total scores will be considered as non-remissions and the subjects with missing HAMD-17 total scores will be included in the denominator of the remission rate.

The remission rate will be compared between the pimavanserin and placebo groups within each stage using Pearson's chi-square test.

Let n be the total number of subjects in FAS1, n_{1q} be the number of placebo subjects in FAS1, n_{1p} be the number of pimavanserin subjects in FAS1, n_{2q} be the number of placebo subjects in FAS2 (i.e., placebo non-responders in Stage 1, were randomized to the placebo group in Stage 2, received at least one dose of study drug in Stage 2, and have both a Baseline [Study Week 5] value and at least one post-Baseline value for the HAMD-17 total score in Stage 2), and n_{2p} be the number of pimavanserin subjects in FAS2 (i.e., placebo non-responders in Stage 1, were randomized to the pimavanserin group in Stage 2, received at least one dose of study drug in Stage 2, and have both a Baseline [Study Week 5] value and at least one post-Baseline value for the HAMD-17 total score in Stage 2).

Let r_{1q} be the number of placebo remission subjects in FAS1 in Stage 1, r_{1p} be the number of pimavanserin remission subjects in FAS1 in Stage 1, r_{2q} be the number of placebo remission subjects in FAS2 in Stage 2, and r_{2p} be the number of pimavanserin remission subjects in FAS2 in Stage 2.

Let $q_1 = r_{1q} / n_{1q}$ and $p_1 = r_{1p} / n_{1p}$ be placebo and pimavanserin remission rate in Stage 1. Let $q_2 = r_{2q} / n_{2q}$ and $p_2 = r_{2p} / n_{2p}$ be placebo and pimavanserin remission rate in Stage 2, among

Statistical Analysis Plan
2018

21 August

placebo non-responders in Stage 1. Let w be the weight for Stage 1 and $1-w$ be the weight for Stage 2 (Note: w is 0.5 for this study).

The null hypothesis is: $w (P_1 - Q_1) + (1 - w) (P_2 - Q_2) = 0$.

The alternative hypothesis is: $w (P_1 - Q_1) + (1 - w) (P_2 - Q_2) \neq 0$.

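### SAP 13.3 gives SF-12, DAI-10 and MGH-SFI two missing-data analyses without naming the main one, and the LOCF version can create a difference when dropout is unequal

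*SAP*

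**What the plan says.** Protocol 9.4.3 fixes the schedule: "For the SF-12, DAI-10, and MGH-SFI, which are assessed only at Baseline and at Week 5 of each stage". The schedules of assessments agree, placing the three scales at Study Weeks 0, 5 and 10.

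SAP 13.3 runs every ANCOVA of these endpoints in two ways. The first uses observed values only. The second uses LOCF, with the note that "for subjects without post-Baseline values, the Baseline values will be carried forward". The stages are then combined with Equation (1). Neither ANCOVA is called main, and the text does not say which one supplies the stage estimates for Equation (1).

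Four further provisions matter:

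- **Full analysis sets (SAP 4).** Entry needs a post-Baseline HAMD-17 value in the stage. A subject can therefore be included with no post-Baseline SF-12, DAI-10 or MGH-SFI.
- **ET data.** The Week 10/ET visit in Protocol 6.5.12 includes the three scales ("SF-12, SDS, DAI-10, MGH-SFI, KSS"). Protocol 4.4 says "Every effort should be made to complete the Week 10/ET visit should a subject discontinue prematurely from the study". SAP 5.3.1 confirms that all assessments, "including the assessments at early termination visits, will be used for planned timepoint analyses".
- **Scoring (SAP 5.2.5 and 5.2.7).** One blank item makes the DAI-10 or MGH-SFI score missing.
- **Testing status (Protocol 9.4.10).** These endpoints are tested at a nominal two-sided 0.05, outside the hierarchy.

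**The concern.** LOCF usually carries a fairly recent on-treatment value. Here the only scheduled earlier value in each stage is that stage's Baseline, so two things can happen to a subject without a Week 5 score.

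- With no ET value, the recorded change is zero and is analysed as if observed. A completer who leaves one DAI-10 or MGH-SFI item blank can be treated the same way.
- With an ET value, that value stands in for Week 5. For MGH-SFI ("The time frame for this scale is the past month") and SF-12 (4-week recall, Protocol 6.2.9), an exit in the first weeks of Stage 1 still largely describes the time before study drug.

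The arm that loses more subjects is thus assigned less change, whether or not the drug works. Every subject in the analysis set has at least one post-Baseline HAMD-17 score in the stage, but neither ANCOVA uses it.

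These scales carry the quality-of-life, drug-attitude and sexual-functioning objectives. With four scores and two analyses each, the plan yields two sets of nominal p-values and no rule for choosing between them.

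**Working it through.** **Inputs from the documents** (SAP 3.5, Protocol 9.5). HAMD-17 mean changes, placebo and pimavanserin: Stage 1, -7.8 and -10 (SD 8); Stage 2, -2.8 and -6.0 (SD 6). Weights 0.5/0.5. There are 168 evaluable subjects, allocated 1:3 in Stage 1 (42 and 126), with 70% placebo non-responders (126 × 0.7 ≈ 88, so 44 and 44).

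**Plan's own figure.** Effect = 0.5 × 2.2 + 0.5 × 3.2 = 2.70. SE = √[0.25 × 64 × (1/42 + 1/126) + 0.25 × 36 × (1/44 + 1/44)] = √(0.508 + 0.409) = 0.958. Power = Φ(2.70/0.958 - 1.96) = 80.5%, which agrees with the stated 80% or more. This concerns HAMD-17; the documents give no such figure for the three scales.

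**Assumptions for the illustration.** HAMD-17 means stand in for the three scales, and the dropout rates are assumed. The 15%/8.3% pair averages 10% under Stage 1's 1:3 allocation (0.25 × 15 + 0.75 × 8.3 ≈ 10). Applied to Stage 2 at 1:1 it averages about 11.7%. The plan's own 10% is a non-evaluable rate, not a dropout rate on these scales.

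**Formula.** Let d be the share of an arm carried forward and f the fraction of the arm's mean change m already reached at the carried value. The arm mean becomes m(1 - d + df). With f = 0, Baseline is carried. Below, improvement is positive and a positive difference favours pimavanserin.

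**No drug effect (placebo means in both arms).** At f = 0 the combined difference is 0.5 × [(1 - d_pim) - (1 - d_plc)] × (7.8 + 2.8). For 15% versus 8.3%: 0.5 × (0.85 - 0.917) × 10.6 = -0.36, or 13% of 2.70.

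**Planned effect present.** For equal 10% dropout at f = 0: 0.5 × [(0.9 × 10 - 0.9 × 7.8) + (0.9 × 6 - 0.9 × 2.8)] = 0.5 × (1.98 + 2.88) = 2.43. For 15% versus 8.3%: 0.5 × [(8.50 - 7.15) + (5.10 - 2.57)] = 1.94, which is 28% below 2.70.

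| Dropout, pimavanserin / placebo | No true effect, f = 0 | No true effect, f = 0.5 | True effect 2.70, f = 0 | True effect 2.70, f = 0.5 |
|---|---|---|---|---|
| 10% / 10% | 0 | 0 | 2.43 | 2.57 |
| 15% / 8.3% | -0.36 | -0.18 | 1.94 | 2.32 |
| 15% / 5% | -0.53 | -0.27 | 1.77 | 2.23 |
| 5% / 15% | +0.53 | +0.27 | 3.10 | 2.90 |
| 8% / 12% | +0.21 | +0.11 | 2.70 | 2.70 |

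Equal dropout creates nothing under the null but shrinks a true effect by the factor 1 - d. Unequal dropout moves the result either way. Carrying half the change halves the shift.

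**Placebo-based imputation (SAP 13.1.2) on the same inputs.** At 10% dropout: Stage 1 = (0.9 × 10 + 0.1 × 7.8) - 7.8 = 1.98; Stage 2 = (0.9 × 6 + 0.1 × 2.8) - 2.8 = 2.88; combined 2.43. At 15% pimavanserin dropout: 0.85 × 2.70 = 2.30. It removes the null-case difference but also dilutes a true effect.

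**The case against.** The strongest reply is that a sound analysis is already planned. The observed-value ANCOVA is listed first, imputes nothing, and is valid if missingness depends only on arm and Baseline. LOCF is then a second look under another assumption. This largely stands, and it limits the point to an unlabelled hierarchy and a weak choice of second analysis.

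A reader might infer three stronger things that the documents do not support.

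- *That LOCF contradicts the plan's own aim.* SAP 12.3 describes the MMRM as aiming at the "treatment effect that would have been observed if all subjects had continued on treatment for the full study duration", but says so only for the primary and key secondary endpoints. Any mismatch with these scales is an inference.
- *That most dropouts will be given zero or very early change.* ET visits are sought, include these scales and enter the analyses. No dropout or ET completion rate is given, so the share cannot be known.
- *That the figures above bound or predict the bias.* The shift scales with the mean change on the scale; a scale that hardly moves on placebo shows almost no null-case shift. Nor is the no-ET case a worst case, since an ET value worse than Baseline would shift the mean further than zero change does.

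It is also fair to say that the placebo-based imputation in SAP 13.1.2 would not by itself cure the dilution, as the 2.43 shows. That is why it is not the main remedy below.

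**Conclusion.** The point holds in a limited form. SAP 13.3 leaves two competing ANCOVAs unranked, and its carry-forward rule, on scales with one scheduled post-Baseline value per stage, can produce a treatment difference without a drug effect. That needs two conditions: dropout that differs between arms, and a scale that changes on placebo. The illustrative size is 0.36 points at 15% versus 8.3% with no ET values, in either direction depending on which arm loses more. It rests on HAMD-17 means and assumed dropout, so it shows the mechanism, not the expected bias on SF-12, DAI-10 or MGH-SFI.

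The LOCF values also enter as if observed, so the analysis carries no imputation uncertainty; that effect has not been sized here. These endpoints carry nominal tests only, so the primary and key secondary conclusions stand whatever is done. This is a low-priority improvement.

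**What to change.** In SAP 13.3:

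1. Name the observed-value ANCOVA as the main analysis of SF-12 PCS and MCS, DAI-10 and MGH-SFI, and state that its stage estimates feed Equation (1).
2. Replace the LOCF version, including the note on carrying Baseline, with multiple imputation under MAR. Do this by arm within each stage, with the scale's Baseline value and the subject's available HAMD-17 scores from that stage in the model. Follow with the same ANCOVA, combination by MIANALYZE, and Equation (1).
3. Optionally add placebo-based imputation in the style of SAP 13.1.2 as a sensitivity analysis, noting that it also dilutes a true effect (2.43 instead of 2.70 at equal 10% dropout in the illustration).

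If MAR holds given those variables, step 2 removes the null-case difference, and it carries imputation uncertainty into the standard error. The cost is SAP wording plus some programming. The HAMD-17 code cannot be reused unchanged, because its 0 to 52 limits do not fit these scales and DAI-10 moves in steps of 2 from -10 to 10. Comparability with older LOCF results is lost. If the sponsor prefers to keep LOCF, step 1 together with labelling LOCF as a sensitivity analysis is the minimum that settles which result counts.

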12.2 Adjustment for Covariates

The corresponding baseline value will be included as a covariate for the analysis of HAMD-17 and SDS mean scores using the mixed model for repeated measures (MMRM) as described in Sections 13.1 and 13.2.

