13. METHODS OF EFFICACY ANALYSES

13.1 Primary Efficacy Analysis

13.1.1 Primary Analysis

The primary efficacy endpoint is the change from Baseline to Week 5 in the Hamilton Depression Scale (17 Items) (HAMD-17) total score.

Let Δ_1 and Δ_2 be the difference in the mean change from Baseline to Week 5 in the HAMD-17 total score between the pimavanserin and placebo groups in Stage 1 and Stage 2 respectively. Let w be the weight for Stage 1 and $1-w$ the weight for Stage 2.

The null hypothesis is: $w\Delta_1 + (1 - w)\Delta_2 = 0$.

The alternative hypothesis is: $w\Delta_1 + (1 - w)\Delta_2 \neq 0$.

The hypothesis testing will be performed using the weighted combination of statistics from the stage-specific MMRM. The MMRMs will include effects for treatment group, visit, treatment-by-visit interaction, Baseline HAMD-17 total score, and the Baseline HAMD-17 total score-by-visit interaction. An unstructured covariance matrix will be used and the Kenward-Roger approximation will be used to adjust the denominator degrees of freedom.

[REDACTED]

In the event that the model fails to converge using the unstructured covariance matrix, the following covariance structures will be modeled in the order given (i.e. from least parsimonious to most parsimonious): heterogeneous Toeplitz, heterogeneous compound symmetry, heterogeneous autoregressive(1), Toeplitz, compound symmetry, autoregressive(1), variance components. The first covariance structure that allows for convergence will be selected for the final model.

Statistical Analysis Plan
2018

21 August

The overall treatment effect will be assessed as the weighted differences between the pimavanserin and placebo groups in least-squares mean change from Baseline to Week 5. The prespecified weight w , is 0.5/0.5 for Stage 1/Stage 2.

Inference will be conducted using the following weighted linear combination of stage-wise treatment effects (Chen et al., 2011 and Fava et al., 2003):

$$Z = \frac{w\hat{\Delta}_1 + (1-w)\hat{\Delta}_2}{\sqrt{w^2\text{Var}(\hat{\Delta}_1) + (1-w)^2\text{Var}(\hat{\Delta}_2)}} \sim N(0, 1) \quad (1)$$

In the above formula, $w = 0.5$ and $\hat{\Delta}_1$ and $\hat{\Delta}_2$ are the differences in least squares (LS) means between pimavanserin and placebo at Week 5, for Stages 1 and 2, respectively.

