Inference will be made using the following weighted linear combination of stage-wise treatment effects:

$$Z = \frac{w(p_1 - q_1) + (1 - w)(p_2 - q_2)}{\sqrt{w^2 \text{Var}(p_1 - q_1) + (1 - w)^2 \text{Var}(p_2 - q_2)}} \sim N(0, 1),$$

$$\text{where, } \text{Var}(p_i - q_i) = \frac{p_i(1-p_i)}{n_{ip}} + \frac{q_i(1-q_i)}{n_{iq}}, \quad i = 1, 2. \quad (3)$$

Treatment response rate at the end of the two 5-week treatment periods

Treatment response is defined as a reduction from Baseline in HAMD-17 total score of 50% or more. The hypotheses and the analysis method for treatment response rate are the same as the hypotheses and the analysis method for the remission rate but with treatment response replacing remission.

Change from Baseline to Week 5 in CGI-S score

The change from Baseline to Week 5 in CGI-S score will be analyzed in a similar way as the primary analysis of the primary efficacy endpoint using the weighted linear combination test with the Baseline HAMD-17 total score replaced by the Baseline CGI-S score.

CGI-I score at Week 5

The CGI-I score will be analyzed in a similar way as the primary analysis of the primary efficacy endpoint using the weighted linear combination test. The differences are (1) the response is CGI-I score (as opposed to the change from Baseline in CGI-I score) and (2) the Baseline CGI-S score will be used as the covariate in the MMRM models.

The CGI-I data will also be dichotomized by combining “very much improved” and “much improved” into 1 category (“Improved”), and the remaining items into the other (“Not Improved”). For analysis purposes, missing CGI-I scores and CGI-I scores of 0 (“not assessed”) will be treated as “Not Improved”.

Statistical Analysis Plan
2018

21 August

The observed score and dichotomized data will be descriptively summarized by treatment group and visit. Treatment comparisons with respect to the dichotomized data within each stage for FAS1 and FAS2 will be performed using Pearson's chi-square test. No overall treatment comparisons combining Stages 1 and 2 will be made with respect to the dichotomized data.

Change from Baseline to Week 5 in SF-12 scores

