The change from Baseline to Week 5 in the norm-based Aggregate Physical Score and the norm-based Aggregate Mental Score will be summarized by treatment group and analyzed within each stage for FAS1 and FAS2 using the analysis of covariance (ANCOVA) model with treatment group as a factor and the corresponding Baseline value as a covariate. The overall treatment effect combining the 2 stages will be tested in a similar way as the primary efficacy endpoint using the weighted linear combination test in Equation (1).

Change from Baseline to Week 5 in DAI-10 score

The change from Baseline to Week 5 in DAI-10 score will be analyzed in a similar way as the SF-12 scores are analyzed.

Change from Baseline to Week 5 in KSS score

The change from Baseline to Week 5 in the 9-point KSS scale score will be analyzed in a similar way as the primary analysis of the primary efficacy endpoint using the weighted linear combination test with the Baseline HAMD-17 total score replaced by the Baseline KSS score.

Change from Baseline to Week 5 in MGH-SFI score

The change from Baseline to Week 5 in MGH-SFI score will be analyzed in a similar way as the SF-12 scores are analyzed.

Change from Baseline to Week 5 in BIS-11 score

The change from Baseline to Week 5 in BIS-11 score will be analyzed in a similar way as the primary analysis of the primary efficacy endpoint using the weighted linear combination test with the Baseline HAMD-17 total score replaced by the Baseline BIS-11 score.

Change from Baseline to Week 5 in SIS score

The change from Baseline to Week 5 in SIS score will be analyzed in a similar way as the primary analysis of the primary efficacy endpoint using the weighted linear combination test with the Baseline HAMD-17 total score replaced by the Baseline SIS score.

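### Remission is compared with crude proportions although stage Baseline HAMD-17 is available for every analysed subject: a small, assumption-dependent loss of precision, not bias

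*SAP*

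**What the plan says.** Remission is an other secondary endpoint. SAP 13.3 sets out its analysis:

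- Definition: "Remission is defined as a HAMD-17 total score less than or equal to 7".
- Within stage: "The remission rate will be compared between the pimavanserin and placebo groups within each stage using Pearson's chi-square test".
- Across stages: "Inference will be made using the following weighted linear combination of stage-wise treatment effects". This is Equation 3, a Z statistic built from raw proportions with the usual binomial variances and w = 0.5.
- Missing data: "Missing HAMD-17 total scores will be considered as non-remissions"; these subjects stay in the denominator.

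No covariate appears in either test, and no adjusted sensitivity analysis of remission is planned.

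The continuous endpoints are handled differently. For HAMD-17 (SAP 13.1.1), "The MMRMs will include effects for treatment group, visit, treatment-by-visit interaction, Baseline HAMD-17 total score, and the Baseline HAMD-17 total score-by-visit interaction". SDS (13.2), CGI-S, KSS, BIS-11 and SIS (13.3) follow the same model with their own baseline, and CGI-I uses baseline CGI-S. SF-12 has an analysis of covariance "model with treatment group as a factor and the corresponding Baseline value as a covariate", and DAI-10 and MGH-SFI follow it.

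SAP 4 requires a HAMD-17 value at Study Week 0 for FAS1 and at Study Week 5 for FAS2, so the covariate is complete in both sets.

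**The concern.** Because remission is a fixed threshold, the fall needed depends on where a subject starts the stage: 15 − 7 = 8 points from a score of 15, but 28 − 7 = 21 points from a score of 28. Baseline severity is therefore expected to be prognostic for remission, and neither randomisation is described as stratified by it (Protocol 9.6.2, SAP 3.3). Using a complete baseline covariate would be expected to narrow the interval for the same marginal risk difference. At stake is some precision on a clinically readable endpoint for which the sample size was not chosen.

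**Working it through.** **1. The plan's own figure.** From SAP 3.5: 168 evaluable, 1:3 allocation, so 42 and 126 in Stage 1. Seventy percent of 126 is 88, so 44 per arm in Stage 2. Differences are 10 − 7.8 = 2.2 (SD 8) and 6.0 − 2.8 = 3.2 (SD 6).

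- Var1 = 64 × (1/42 + 1/126) = 2.03; Var2 = 36 × (2/44) = 1.64
- Z = 0.5 × (2.2 + 3.2) / √[0.25 × (2.03 + 1.64)] = 2.7/0.958 = 2.82
- Power = Φ(2.82 − 1.96) = 80.5%, as stated for the primary endpoint.

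The documents give no power, rate or variance for remission.

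**2. Assumptions.** The documents also give no baseline HAMD-17 mean or SD and no baseline-to-Week-5 correlation. The check uses a normal model with the plan's changes and SDs, and remission at a score of 7 or below. Holding the Stage 1 change SD at 8, the Week 5 SD is s_Y = ρs_B + √[(ρs_B)² + 64 − s_B²] and the slope is ρs_Y/s_B. For s_B = 4:

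- ρ = 0.2: s_Y = 0.8 + √48.64 = 7.77, slope 0.39
- ρ = 0.3: s_Y = 1.2 + √49.44 = 8.23, slope 0.62
- ρ = 0.4: s_Y = 1.6 + √50.56 = 8.71, slope 0.87
- ρ = 0.5: s_Y = 2.0 + √52 = 9.21, slope 1.15

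**3. Large-sample variance reduction**, 1 − Var(adjusted)/Var(Equation 3). The grid was baseline mean 20–26, SD 3–5, ρ 0.2–0.5, and Stage 2 slope of change on baseline −0.5 to 0. Combined difference: 2–6% at ρ = 0.2, 3–8% at 0.3, 6–10% at 0.4, 10–13% at 0.5. By stage: 1.5–15.5% in Stage 1 and 2.4–11.6% in Stage 2.

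**4. At the planned sample sizes**, with a linear model (treatment, baseline) and robust SE; baseline SD 4; 6,000 trials per entry. Variance reductions are under the plan's effects, with the no-effect value in brackets.

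| Baseline mean, ρ | Combined | Stage 1 | Stage 2 | Power, crude → adjusted | Type I error, crude → adjusted |
|---|---|---|---|---|---|
| 22, 0.2 | 2.4% (0.6) | 1.4% (0.4) | 3.4% (1.3) | 41.7 → 41.5% | 5.9 → 5.7% |
| 22, 0.3 | 3.7% (3.4) | 4.2% (3.6) | 3.4% (1.5) | 37.6 → 38.3% | 5.6 → 5.6% |
| 22, 0.4 | 6.3% (6.5) | 7.6% (7.8) | 4.1% (2.4) | 36.0 → 37.5% | 5.8 → 5.2% |
| 22, 0.5 | 9.8% (9.1) | 13.2% (12.2) | 3.1% (2.7) | 32.9 → 35.6% | 5.7 → 5.4% |
| 26, 0.3 | 2.9% (1.9) | 3.7% (2.1) | 1.2% (1.0) | 24.0 → 24.2% | 6.6 → 6.3% |
| 26, 0.5 | 8.3% (8.0) | 10.5% (9.4) | 0.5% (−0.2) | 19.4 → 20.4% | 5.8 → 5.7% |

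Except at ρ = 0.2, where both stages gain little, the reduction comes mainly from Stage 1. Under the plan's effects, Stage 2 placebo remitters average 0.5–2.7 of 44. That arm has none in 7–11% of trials at baseline mean 22 and in 46–60% at mean 26.

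**5. Choice of method.** A standardised logistic risk difference was simulated with baseline SD 4–5 and slopes 0.5–1.0. Under the plan's effects it reduced the combined variance by 3–12%, with the mean difference unchanged to within 0.001. A repeat of those settings gave variance ratios of 0.88–0.98. With no effect the ratio was 0.93–1.02 combined and 1.01–1.10 in Stage 2 alone. The Stage 2 fit failed to converge in 12–20% of trials under the effects and 22–37% under none. Type I error was 5.6–6.7%, against 5.3–5.9% for the crude test. Linear adjustment with robust SE, under similar assumptions, gave ratios of 0.90–0.98 with and without an effect, and type I error of 4.8–5.7% against 5.4–6.3% crude.

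**6. Limit of the model.** It yields about 48–49% placebo non-responders at baseline mean 22 and 65–68% at mean 26, against the plan's 70%. Stage 2 in step 4 was held at 44 per arm. The rows at mean 26 are closest to the plan and show the smallest Stage 2 gain.

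**The case against.** The strongest case is that nothing here is wrong. Equation 3 is a valid large-sample test of its stated null under randomisation. Protocol 9.4.3 left the binary methods to the SAP. SAP 12.2 commits to covariates only in these terms: "The corresponding baseline value will be included as a covariate for the analysis of HAMD-17 and SDS mean scores". The binary endpoints are treated alike: "The hypotheses and the analysis method for treatment response rate are the same as the hypotheses and the analysis method for the remission rate", and dichotomised CGI-I is also unadjusted. The HAMD-17 change, which is the more powerful question, is already adjusted. Plain logistic adjustment could also do harm in Stage 2. All of this stands, and it makes the point one of efficiency.

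A reader might infer that, without stratification, a chance severity imbalance biases the crude difference. The documents do not support that. With SD 4 the standard error of the Stage 1 baseline difference is 4 × √(1/42 + 1/126) = 0.71 points. Modelled placebo remission at baselines 18 and 26 is 25% and 14% (ρ = 0.2) or 40% and 8% (ρ = 0.5), that is 11/8 = 1.4 to 32/8 = 4 percentage points per HAMD-17 point. A one-SE imbalance thus moves the crude difference by about 1 to 3 percentage points, but that is ordinary random error and Equation 3's variance already includes it. Adjustment removes part of that error; it does not correct a fault.

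What the objection does not answer is why a complete baseline score, used for every continuous endpoint, is left unused here when a stable method exists.

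**Conclusion.** The point holds as a minor loss of precision. Over the assumptions tried, baseline adjustment lowers the variance of the combined remission difference by roughly 1 to 13%. The low end is the finite-sample result at ρ = 0.2 with no effect; the high end is the large-sample result at ρ = 0.5. The corresponding large-sample power gain is 0.4 to 4.7 points (median 2.0) on a crude power of about 22 to 47%, so the endpoint stays underpowered either way.

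It would be tempting to say that the plan gives up a fixed share of variance at no cost, or that baseline strongly determines remission. Neither follows from the documents. They contain no baseline SD, slope or remission rate, and in Stage 2 adjustment brings little or nothing and needs a safeguard. Nor does the case extend to response, which is already relative to baseline: adjusting it ranged from a 5% gain to a 1% loss. Remission is tested at a nominal 0.05 outside the hierarchy (Protocol 9.4.10), so no primary or key secondary conclusion is affected.

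**What to change.** Before unblinding, amend SAP 13.3 for remission only:

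- In each stage, estimate the risk difference adjusted for stage Baseline HAMD-17. Choose one method in advance: a linear model with treatment and baseline and a robust SE, or a standardised logistic risk difference with a named SE method. The logistic route needs a fixed rule that reverts to the crude stage difference when an arm has fewer than a stated number of remitters. The linear route is simpler and held its size at least as well as the crude test in the simulations.
- Combine the stages with w = 0.5 as now.
- Keep missing scores as non-remissions.
- Report the crude Equation 3 test as a sensitivity analysis.

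The cost is a paragraph of SAP text, a few lines of code and, for the logistic route, a sparse-cell threshold to settle in advance. No new data are needed, and no protocol text is contradicted. The return is a small gain on one other secondary endpoint, so leaving the plan as it is would be defensible.
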